5.4.2.5 Conclusion

The results from both adult (Phases I-III) and pediatric Phase I trials of high-dose oral fenretinide suggest that peak plasma levels exceeding 10 µM can be achieved with tolerable toxicity.

Prolonged periods of fenretinide treatment (up to 5 years) in the cancer prevention studies were associated with fenretinide steady-state peak plasma concentrations of 1-2 μ M at daily doses of 200 to 400 mg and no significant toxicity/safety concerns. In the cancer treatment studies in children the peak plasma concentrations reached 14.5 μ M with relatively mild adverse effects. In general, no significant toxicity was observed in children with peak plasma levels below 3μ M. The incidence and severity of the most commonly

observed toxicities related to fenretinide treatment such as nyctalopia, headache, dry eye, cutaneous, ungual, or mucosal toxicities observed in patients with 3–10 μ M peak levels increased at peak levels >10 μ M. The adverse events were resolved after dose reduction or after discontinuation of the treatment. Maximum tolerated dose was not reached in children with neuroblastoma at daily doses of 4000mg/m² and fenretinide plasma peak levels of 14.5 μ M.

Fenretinide reduces plasma retinol levels and retinol binding protein potentially leading to development of symptoms of nyctalopia in some patients. This effect was rarely dose limiting, and quickly reversible following dose reduction or discontinuation of treatment. Moreover, this effect does not seem to be proportional to the dose. In previous fenretinide clinical studies a drug free period of 3-7 days following a 28-day oral exposure was proven to help prevent or alleviate nyctalopia and was integrated in all clinical studies.

Based on the Phase Ib study data in adult CF patients, the dose of 300mg/day (equivalent to 800 mg/day of corn-oil formulation of fenretinide) resulted in steady state 8-hour plasma concentration of fenretinide on Day 21 of 2.7 µM and average drug plasma concentration of 2.06 µM, at the upper range of "low doses". There were no serious adverse events related to fenretinide recorded in the study, and the overall number of adverse events tended to decrease with the increase of the dose. The incidence of nyctalopia symptoms reported in this study is consistent with the incidence of symptoms of diminished dark adaptation reported in other clinical trials with fenretinide. Ad-hoc and scheduled ophthalmological examinations did not reveal any abnormality or signs of retinal damage in these patients. The reduction of serum retinol levels, as compared to baseline, appears to be smaller in CF patients than other patient populations for which lower doses of fenretinide were used.

The recently completed APPLAUD Phase 2 clinical trial also has an aggregated safety profile compatible with the severe nature of CF disease, and does not reveal a concerning safety signal, as evidenced by the favorable decisions rendered by the independent Data Monitoring Committee on five occasions.

Of direct relevance for the expansion of the RESOLUTION trial is the confirmation of a good safety profile in the 117 patients who received LAU-7b therapy so far, and most favorable in the proposed subset of patients for the expansion, those with a Heath Status of 3 or 4 (Moderate-to-Severe COVID, n=76). The positive efficacy signal seen across several endpoints in these subgroups is a good justification for expanding the enrollment of such patients, presently underserved by treatment option to prevent the onset of respiratory failure.

Moreover, with antivirals such as Paxlovid[®] and molnupiravir and the past usage of neutralizing antibodies, which are all used in an outpatient setting, a successful outcome of the expanded RESOLUTION trial will bode well for a once-a-day treatment option which can be administered to the underserved moderate to severe hospitalized COVID-19 patient population, allowing patients to continue the treatment at home after discharge from the hospital.

These collective results are supporting the safety of the selected Initial Treatment and Follow-up Treatment dose of 300 mg and 200 mg/day, respectively with LAU-7b formulation in this Phase 2 study in adults with COVID-19 disease, to exert the maximal antiviral activity and the pro-resolving effects on inflammation.

5.4.3 Specific Rationales for the proposed expansion of this Phase II study

5.4.3.1 Design/Structure and Dosing Regimen

This Phase 3 study extension aims at confirming the positive efficacy signal observed with LAU-7b in patients with COVID-19 disease susceptible to aggravate owing to the presence of risk factors. In the pilot portion of the study, patients with a baseline Health Status of 3 or 4 (not in respiratory failure) showed a clear

benefit while patients with a Health Status of 5 (in respiratory failure) did not. This justifies not pursuing the latter in the study expansion but pursuing in the Moderate-to-Severe COVID patients. It will guide further development in larger well-controlled clinical trials.

Since time is of the essence during the COVID-19 pandemic to identify useful treatments for affected patients, the study is simple in design, is short in duration and makes use of assessments commonly done in patients hospitalized for the disease. The primary objective of the study remains to measure the impact of LAU-7b on the recovery rate and on the frequency, severity and timing of COVID-19 disease aggravation and outcomes.

This is a randomized, double-blind (patients, Investigators and blinded study staff), placebo controlled, Phase II/III study (details are presented in Section 7.2). This study is randomized and placebo-controlled to reinforce its conclusiveness and the robustness of its outcomes.

There will be no active control treatment but patients will undergo the Standard of Care at their institution. A randomized, double-blind study design will avoid observer bias and reduce symptoms or outcomes arising from the patients' knowledge of treatment. A parallel design is most appropriate for this type of acute indication and with a short impactful period.

While the Phase Ib study with fenretinide was conducted in adult CF patients and there is a Phase 2 in the CF indication in adult CF patients which showed a positive signal of efficacy, the treatment paradigm for the treatment of COVID-19 disease is very different; it is a short, one-time 14-Day usage while the CF indication calls for longer term chronic administration.

5.4.3.2 Rationale for dose selection:

In the previous Phase Ib study in CF, three doses of LAU-7b were investigated and all showed good tolerability. Doses for that study were chosen based on the enhanced bioavailability that LAU-7b capsule formulation conferred to fenretinide, the active product ingredient,

In essence, the Phase Ib was a concentration-driven study, while aiming at finding a maximum tolerated dose. On the exposure standpoint, the Phase Ib dose of 200 mg (middle dose) achieved the average circulating level (circa 2 μ M Css) which corresponds to the concentrations eliciting the cytokine storm protection in the mice model of sepsis (1-2 μ M) ³⁷ and close to the IC50 for the antiviral activity against the MERS-CoV virus (2.8 μ M)⁴¹ and the SARS-CoV-2 virus

Because CF patients have a different pharmacokinetic profile than other patient populations, usually requiring higher doses, it is expected that in COVID patients, the 300mg dose should achieve a concentration slightly higher than seen with CF patients, and this is why this dose will be administered in the first three days, for a faster onset of a concentration eliciting antiviral effect.

The maintenance dose of 200 mg, administered on Days 4-14, is expected to maintain a plasma concentration expected to have both antiviral activity and a pro-resolving effect on inflammation. Since a low LAU-7b dose is used in this study, no dose reductions are planned.

The administration of the study treatment is split in two regimens:

1. Initial Treatment (Days 1-3) is given to all randomized patients in order to start the treatment as early as possible. The Initial Treatment daily dose is higher (300 mg) for a faster onset of a concentration eliciting antiviral effect.

2. Follow-up Treatment (Days 4-14) is lower (200 mg) to maintain plasma concentrations that support both antiviral and inflammation-controlling effects.

The study regimen is justified by the good safety profile observed in the 117 patients who received it so far, even more favorable in the proposed subset of patients for the expansion, those with a Heath Status of 3 or 4 (Moderate-to-Severe COVID, n=76).

This expanded study is now intended to be confirmatory for hospitalized moderate-to-severe COVID-19 patients who are at risk to progress to respiratory failure, in order to inform further development and potentially support an Emergency Use Authorization application.

5.4.3.3 Rationale for Study Assessments

The study assessments are generally part of the SOC for patients hospitalized for suspected or confirmed SARS-CoV-2 infection with the presence of underlying conditions or measurement associated with a greater risk of complications. Most are frequently assessed during hospitalization and includes vital signs, symptom check, safety laboratory tests, assessing the need or not for supplemental oxygenation or for a transfer to the intensive care unit (ICU), as well as determining if hospitalization can end (patient discharge). It is recognized that during the pandemic, institution/departmental policies for preventative reasons can change very rapidly and affect the hospitalization thresholds.

EQ-5D-5L Quality of Life questionnaire: This questionnaire is a well-documented scoring system that have been widely used and validated as QoL assessment tool for this type of population. It will be filled at screening and by fully eligible patients (confirmed SARS-CoV-2 infection) reaching Days 14, 29 and 45 (and at the longer term safety/QoL assessment, around 2 months after study start), and able to fill the questionnaire. This is not part of Standard of Care, but this is relevant for outcomes since patients with varying degrees of functionality will represent a variable pharmacoeconomic weight.

Scoring the Heath Status of the patients using the ordinal scale: Performed on specific days by the study coordinators or other delegated and trained staff, this assessment aims at formally determine in which category the patient is, each period of 24 hours (a study Day) once at a time. This is not done as part of SOC, but is key for this study. Several variables are derived from it.

Serial oropharyngeal swabs to detect SARS-CoV-2 virus: This was an optional objective measurement of the virus presence and allows to determine how long the virus shedding lasts from the oropharyngeal cavity. Unfortunately, none of the clinical sites volunteered to perform it due to the complexity of accessing repeatedly the patient on the COVID wards and the lack of resources. This assessment will not be pursued in the expansion of the study.

6 STUDY OBJECTIVES

Primary objective:

To evaluate the efficacy of LAU-7b therapy + Standard-of-Care (SOC) relative to placebo + SOC in patients with COVID-19 disease with confirmed SARS-CoV-2 infection (target population).

Secondary objectives:

1- To assess the safety of LAU-7b therapy in all patients who received at least one dose of the study medication (Safety Population), compared to placebo + SOC.

- 2- To assess the efficacy of LAU-7b therapy at decreasing the rate of COVID-19 disease related aggravation in the target population (such as a worsening of one category on the ordinal scale, onset of severe categories on the ordinal scale, need for transfer to Intensive Care Unit (ICU), need for mechanical ventilation and death, among others), compared to placebo + SOC.
- 3- To measure the impact of LAU-7b therapy on the time course of the COVID-19 disease in the target population, as depicted by mean ordinal scale change from baseline at each assessment time, and by time-to-event analyses (time to an improvement of one category on the ordinal scale, time to recovery (defined), time to ICU transfer, time to mechanical ventilation, and time to death), compared to placebo + SOC.
- 4- To assess the benefit of LAU-7b therapy on the Quality of Life, compared to placebo + SOC.

Rationale for the selection of objectives:

The primary objective of this study has been selected because it is simple and clinically relevant; what impact LAU-7b therapy has on hospitalized patients in terms of outcomes by Days 29 and 60 post-randomization. In the context of limited ICU resources and equipment, any reduction in the burden of intensive care, in particular invasive mechanical ventilation or ECMO, will free up resources and have a huge pharmacoeconomic impact. Moreover, since patient who remain mildly affected recover more rapidly from COVID-19 disease, it allows a better flattening of the prevalence as a function of time.

The secondary objectives, besides safety, are aligned with the properties of LAU-7b/fenretinide demonstrated in humans and preclinical studies, such as the protection from an excessive pro-inflammatory response, the promotion of the resolution of inflammation and the demonstrated antiviral properties.

This will help guiding further development of LAU-7b in the treatment of COVID-19 disease, and may also contribute to its development in CF, due to the possible commonality between CF Pulmonary Exacerbations and the exaggerated inflammatory response seen in aggravated COVID-19 patients. Furthermore, the knowledge derived from this study may find applications with other acute infections causing dysregulated inflammation in the lung.

7 STUDY DESIGN

7.1 Endpoints

7.1.1 Efficacy Variable:

The main efficacy variable is the 7-point ordinal scale of the patient status. The ordinal scale is presented below, and categories 1-6 are further detailed/clarified to help categorization at baseline:

Ordinal Scale

- 1. Not hospitalized, no limitations on activities
 - a. Able to carry on regular daily activities;
 - b. May experience light symptoms that do not interfere with daily activities.
- 2. Not hospitalized, limitation on activities
 - a. Cannot carry on daily activities like prior to COVID-19;
 - b. Lingering symptoms of sufficient intensity to interfere with daily activities;
 - c. Periods of rest during the day to help recovery.
- 3. Hospitalized (under observation/admitted), not requiring supplemental oxygen

- a. Remain bedridden most of the day;
- b. Ambulates without significant help;
- c. Under room air, able to maintain oxygen saturation at 93% and above;
- d. Does not require oxygen cannula, even at low flow of oxygen.
- 4. Hospitalized (under observation/admitted), requiring supplemental oxygen at ≤4 L/min ¹
 - a. Remain bedridden most of the day;
 - b. Ambulates with help;
 - c. Unable to maintain an adequate oxygen saturation.
- 5. Hospitalized, on non-invasive ventilation or high flow oxygen supplementation at >4 L/min
 - a. Bedridden:
 - b. Does not ambulate easily and requires help;
 - c. Unable to maintain an adequate oxygen saturation with a cannula at an oxygen flow ≤4 L/min., or
 - d. Requires non-invasive ventilation with instruments such as a Continuous Positive Airway Pressure (CPAP) machine to maintain adequate oxygen saturation.
- 6. Hospitalized, on invasive mechanical ventilation or ECMO (extra-corporeal membrane oxygenation);
 - a. Bedridden in ICU
 - b. Intubated and connected to a mechanical ventilator, or
 - c. Connected to an ECMO.
- 7. Death.

The ordinal scale is an assessment of health status on a given study day, identifying the worst health status during the previous day of observation. Each day, according to local practice in terms of time of assessment, the worst health status during the previous day gets scored with the scale and will be recorded. i.e. on Day 3, the worst Day 2 health status is obtained, scored and recorded as Day 2 score in the CRF, with the assessment time.

7.1.2 Primary Efficacy Endpoint

The revised primary efficacy endpoint is the proportion of patients requiring mechanical ventilation AND/OR deceased (all causes) by Day 60, compared between the active and control (placebo) arms of the study using the 7-point ordinal scale described above.

Justification for the main Efficacy Variable and the revised Primary Efficacy Endpoint

LAU-7b is proposed to act through a multi-prong approach against COVID-19 disease. It is hypothesized that these effects will reduce the odds of aggravation for the at-risk population that is under observation/admitted at the hospital for the COVID-19 disease. This will translate in a higher proportion of patients that recover and are discharged earlier from the hospital compared to those treated with the SOC alone + placebo. The use of the 7-point Ordinal Scale proposed by the World Health Organization for COVID-19 clinical trials is ideally suited for establishing the proportion of patients requiring invasive mechanical ventilation (and this includes ECMO) AND/OR deceased (all causes) (WHO Ordinal Scale scores 6-7 inclusively) as primary endpoint, particularly if assessed regularly during the course of the study. The time course of the COVID-19 disease is quite short but its complications are devastating and entail a huge burden on caretakers. This efficacy variable and the proportion of patients requiring mechanical

LAU-7b for the treatment of COVID-19 disease in Adults

¹ Patients receiving up to 6L/min with a low-flow device can also qualify as an Ordinal Scale "4" if they have a pre-existing health condition (COPD, heart failure, for example) that causes higher oxygen supplementation needs and if the Investigator judges that the patient is NOT in respiratory failure. Other patients are subject to the <4L/min threshold.

ventilation AND/OR deceased (ordinal scale scores 6-7 inclusively) by Day 60, coined here as the revised primary efficacy endpoint, will permit both an overall picture of the impact of LAU-7b on patient outcomes, and a clinically meaningful assessment of the impact of LAU-7b on the proportion of patients avoiding the invasive mechanical ventilation and/or death.

In addition, changes in the health status depicted by the Ordinal Scale category changes will permit to derive several secondary endpoints listed below.

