9.2.5 Contacts on Days 29 and 45 (window of +/- 3 days)

(not a preset visit number)

The following assessments will be done, either by phone or using an electronic platform compatible with mobile phones or tablets. Based on the patient responses, actions may be taken including inviting the patient to visit the hospital or meet a health professional.

- a. Concomitant medication verification, including any supplemental oxygen currently in use including the oxygen flow;
- b. COVID-19 symptom check (including but not limited to, myalgia, coughing, smell and taste alteration, headache, gastrointestinal disorders...etc.) as per SOC;
- c. Health status determination using the 7-point ordinal scale;
- d. Quality-of-Life questionnaire: EQ-5D-5L questionnaire;
- e. Asking safety-focused open-ended questions:
 - i. How is your health today?
 - ii. How is your vision today?
 - iii. How is your skin today?
- f. Adverse event verification and follow-up on ongoing adverse events.

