10 EFFICACY ASSESSMENTS

10.1 Health Status using the 7-point Ordinal Scale

This is the main efficacy variable of the study. It will be assessed post-randomization daily in hospital as listed in the Schedule of Events, page 11, and on Day 14 (or assessed upon discharge if discharged earlier than Day 14), and at each of the outpatient contacts (once every 3 days up to Day 29, and on Days 45 and 60). The ordinal scale is an assessment of the health status on a given study day, identifying the worst health status during the previous day of observation. Each day, according to local practice in terms of time of assessment, the worst health status gets scored on the Ordinal scale for the previous day and the score will be recorded. i.e. on Day 5, the worst Day 4 health status is scored and recorded as Day 4 score in the CRF. The scale is as follows and further details on each of the categories 1-6 are presented in 7.1.1.

- 1. Not hospitalized, no limitations on activities
- 2. Not hospitalized, limitation on activities;
- 3. Hospitalized (under observation/admitted), not requiring supplemental oxygen;
- 4. Hospitalized (under observation/admitted), requiring supplemental oxygen at ≤4 L/min³;
- 5. Hospitalized, on non-invasive ventilation or high flow oxygen supplementation at >4 L/min;
- 6. Hospitalized, on invasive mechanical ventilation or ECMO (extra-corporeal membrane oxygenation);
- 7. Death.

3

³ Patients receiving up to 6L/min with a low-flow device can also qualify as an Ordinal Scale "4" if they have a pre-existing health condition (COPD, heart failure, for example) that causes higher oxygen supplementation needs and if the Investigator judges that the patient is NOT in respiratory failure. Other patients are subject to the ≤4L/min threshold.

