11.1.3 Serious Adverse Events

SAEs are generally any AEs that result in one or more of the following:

- Fatal (death, regardless of cause, that occurs during participation in the study or occurs after participation in the study but within 30 days post-study (Day 90), and is suspected of being a delayed toxicity due to administration of the study drug);
- Is immediately life threatening (i.e., presents an immediate risk of death at the time of the AE, not an AE that hypothetically might have caused death if it were more severe);
- Requires or prolongs inpatient hospitalization*;
- Causes persistent or significant disability/incapacity;
- Is a congenital anomaly/birth defect;
- Other important medical events that may not be immediately life threatening or result in death or hospitalization but, based upon appropriate medical judgment, are thought to jeopardize the patient and/or require medical or surgical intervention to prevent one of the outcomes defining an SAE**.
- *An inpatient hospitalization is defined as an admission for any length of time. In this specific case of COVID-19 patients already hospitalized, other hospitalization for routine or planned clinical procedures, prolongation of hospitalization for any COVID-19-related adverse change in the patient's condition, or for "social" reasons, should not be considered an AE and should not be reported as a SAE.
- ** While prolongation of hospitalization and/or transfer to Intensive Care Unit per se shall not be considered a AE/SAE, if invasive mechanical ventilation/ECMO is started, the cause for it is an important medical event and therefore reaches the criteria of seriousness to be reported as a SAE.

Definition of Life-Threatening Adverse Experience:

An adverse experience is life threatening if the patient was at immediate risk of death from the event as it occurred (i.e., it does not include a reaction that, had it occurred in a more serious form, might have caused death). For example, drug-induced hepatitis that resolved without evidence of hepatic failure would not be considered life threatening, even though drug-induced hepatitis can be fatal.

Definition of Disabling/Incapacitating Experience:

An adverse experience is incapacitating or disabling if the experience results in a substantial and/or permanent disruption of the patient's ability to carry out normal life functions.

Medical Monitor:

[name], MD

Laurent Safety Line: [contact]

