Using the proportion of patients requiring mechanical ventilation AND/OR deceased by Day 60 in the pilot portion of the study, an effect size of 7% change (i.e. 7% in the control group vs. 0% in the investigational group), comparing the active arm versus the control (placebo) arm, and a minimum of 90% statistical power of detecting a difference of 7% using a two-tailed Fisher Exact test, with a nominal alpha of 0.05, a total sample size of 264 patients (132 per arm) with a Heath Status score of 3 or 4 at baseline is required for the Phase 3 confirmatory portion of this study.

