The primary analysis for the primary endpoint will treat missing observations as is without any imputation, i.e. Including all patients with available health status/survival data at Day 60 for the primary analysis. This is the complete case analysis.

The results from this approach will be presented as the primary analysis in the CSR, while the original analysis using the imputation method specified in the protocol and the SAP will still be included in the CSR, but referred to as the "former planned primary analysis".

3. Additional Analyses

The updated imputation method is defined as follows:

- For the primary analyses on the intent-to-treat (ITT) population, missing observations will not be imputed.
- The original method, which assigned missing observations to non-response (health status 6-7), will continue to be reported as part of the CSR to ensure full transparency.
- The sensitivity and supplementary analyses will remain the same.
- The table numbering follows the ICH E3 guideline for CSR. Since both the pilot study and the extension study are included in the CSR, along with the additional tables described in this SAP addendum, the numbering rule is described as follows:
 - o Main tables from the pilot study are numbered without any suffix.
 - Main tables from the extension study are numbered with the suffix "e".
 - Additional tables described in this SAP addendum are numbered with ".1e" replacing the suffix "e".
- The impacted tables to be differentiated from the main tables in the extension study are listed below:
 - Table 14.2.1.1.1e Primary Analysis: Proportion of Patients Requiring Mechanical Ventilation (includes ECMO) and/or Deceased by Day 60 – ITT;
 - Table 14.2.1.4.1e Supplemental Analysis: Proportion of Patients Requiring Mechanical Ventilation (includes ECMO) and/or Deceased by Day 60 Analyzed by Logistic Regression;
 - Table 14.2.3.1.1e Proportion of Patients Alive and Free of Respiratory Failure on Day 29 ITT;
 - Table 14.2.3.2.1e Proportion of Patients Alive and Free of Respiratory Failure on Day 29 PP;

Status: Version 1.0

Protocol Number: LAU-20-01

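### The addendum's complete-case primary analysis, read literally, excludes a patient with documented ventilation before Day 60 whose Day 60 status is missing, although the cumulative endpoint is already met.

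*Protocol*

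**What the plan says.** **Endpoint.** Protocol 7.1.2 defines the proportion of patients ventilated and/or dead by Day 60, "compared between the active and control (placebo) arms of the study using the 7-point ordinal scale described above". The synopsis equates this with scores 6 and 7.

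**Instrument.** Protocol 10.1 describes each score as "identifying the worst health status during the previous day of observation". Contacts run every 3 days (±2) up to Day 29 (9.2.4), then on Days 45 and 60 (9.2.5, 9.2.6). For patients still in hospital after Day 14, 10.1 speaks of daily scoring, while the Schedule of Events and 9.2.4 give every 3 days.

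**Other records of ventilation.** Protocol 11.1.3 states that "if invasive mechanical ventilation/ECMO is started, the cause for it is an important medical event and therefore reaches the criteria of seriousness". Section 8.3 requires survival and invasive-ventilation status up to Day 60 for every randomized participant, including those who withdraw, where local guidelines permit.

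**Missing data.** Protocol 12.4 (Table 3) and 12.7.1 count missing observations as non-response, which Table 3 equates with scores 6-7. The SAP addendum (Sections 1 and 2), written after results were released on 14MAR2024, makes a complete-case analysis primary: "Including all patients with available health status/survival data at Day 60 for the primary analysis". The protocol's analysis stays in the CSR under another label.

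**The concern.** A cumulative endpoint is settled once its event occurs; later loss to follow-up cannot undo it. The addendum selects patients by whether Day 60 data exist and makes no exception for someone with an event already on record. That removes a known outcome, which is a different matter from declining to impute an unknown one.

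The second, smaller issue concerns the source of the event. If only scheduled scores were used, a survivor ventilated entirely between scored days after Day 29 would never show a 6. The protocol collects the information elsewhere, but no supplied text links those records to the endpoint.

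The test turns on a handful of events, so one misplaced patient can matter.

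**Working it through.** **1. The plan's own figure.** Inputs from Protocol 12.1: "an effect size of 7% change (i.e. 7% in the control group vs. 0% in the investigational group", two-sided Fisher exact test, alpha 0.05, 132 per arm.

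With x placebo events, no active events and equal arms, p = 2·C(132,x)/C(264,x):
- x = 5: p = 0.060
- x = 6: p = 0.029

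Significance therefore needs at least 6 placebo events. Power = P(X ≥ 6), X ~ Binomial(132, 0.07) = 90.6%, and 131 is the smallest number per arm reaching 90%. The stated 264 reproduces. Expected placebo events are 132 × 0.07 = 9.24. At six events in total the expected count per arm is 6 × 132/264 = 3, below 5, so 12.7.1 calls for Fisher.

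**2. One patient under each rule.** Take a patient ventilated on Day 5, extubated and lost on Day 40 (an invented case).
- Endpoint as worded: event.
- Protocol 12.4 and 12.7.1: event, because a missing observation counts as scores 6-7.
- Addendum Section 2, read literally: not analysed.

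A patient known to have died has survival data at Day 60 and stays in. Those exposed are patients with recorded ventilation and no known status at Day 60.

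**3. What one lost placebo event does at the threshold.** Start from 6/132 v 0/132, p = 0.029.
- Patient kept but scored as a non-event: 5/132 v 0/132, p = 0.060.
- Patient excluded, and one event-free active patient also missing: 5/131 v 0/131, p = 2·C(131,5)/C(262,5) = 0.060.
- Patient excluded, nobody missing on active: 5/131 v 0/132. The observed table has probability C(131,5)/C(263,5) = 0.0295. The opposite extreme has C(132,5)/C(263,5) = 0.0306, which is larger and so is not added under the usual two-sided definition; p = 0.029.

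So a single exclusion can, but need not, reverse the conclusion; it depends on the numbers analysed in each arm. An affected active-arm patient would shift the result in favour of the drug.

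**4. The scoring gap.** Taking the scored day as the contact day minus one, and ignoring visit windows, only Days 44 and 59 are scored among the 31 days from Day 30 to Day 60. If only scheduled scores counted and start days were uniform over Days 30-59 (assumed), the share of episodes missed would be:
- 3-day episodes: 24/30 = 80%
- 7-day: 16/30 = 53%
- 10-day: 10/30 = 33%
- 14-day: 2/30 = 7%

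For starts on Days 15-28 with contacts exactly 3 days apart, no episode of 3 days or longer is missed. Deaths are never missed this way, because category 7 persists to the next contact.

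**5. How many events the gap could touch.** In the pilot's placebo patients with Health Status 3 or 4, 5/72 were ventilated and 4/72 died (Protocol 5.4.2.1). The composite was 6.9% (12.1), that is 5/72, so all four deaths lie among the five composite events and one event was in a survivor. At that share, 9.24 × 1/5 = 1.85 expected placebo events would be in survivors. The documents do not say when events occur or how long ventilation lasts.

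**The case against.** The endpoint is worded as any ventilation or death by Day 60, and nothing supplied restricts events to scheduled scores. Section 8.3 demands ventilation status over the whole period, 11.1.3 makes the cause of ventilation reportable, adverse events are checked at every contact through Day 60, and 12.7.2 plans to analyse days under ventilation, which scores on Days 45 and 60 alone could not supply. The main SAP of 29SEP2023 may contain the derivation and is not available. The disease course is described as short, so late survivor episodes may be rare.

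Most of this stands against the scoring-gap issue. A reader might infer that an episode between contacts is not counted; the documents do not say that. They leave the derivation unspecified. Nor is scoring sparse before Day 29, where contacts come every 3 days.

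A reader might also infer a large loss of power: if one or two of nine placebo events were missed, power at 132 per arm would fall from 90.6% to 83.6% or 73.0%. The arithmetic is right but the premise is not supported. At the pilot's survivor share, even if every survivor event began after Day 29, 7-day episodes would lose 1.85 × 16/30 = 0.99 events and 10-day episodes 1.85 × 10/30 = 0.62. The share rests on five events, so it is only a guide.

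These replies do not answer the addendum issue. It does not depend on contact frequency or length of ventilation, and the current addendum text offers no exception for a documented prior event. What does soften it is 8.3: if follow-up was obtained as required, few patients, perhaps none, are affected.

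**Conclusion.** The concern holds for the addendum: taken literally, its inclusion rule excludes patients whose primary event is already documented, and so contradicts the endpoint it analyses. The number of such patients, their arm and hence the direction of any shift are unknown. A change of one event at the significance boundary (6 v 0 to 5 v 0) moves p from 0.029 to 0.060 when the arms analysed are equal in size. No power loss can be stated, because event timing, ventilation length and loss after ventilation are not given.

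The scoring gap is a secondary point about an unstated derivation. It is limited to survivors ventilated wholly between scored days, mainly after Day 29, and the main SAP may already resolve it. The texts on in-hospital scoring after Day 14 also need to be reconciled.

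**What to change.** State in the addendum and CSR that:
- any invasive ventilation, ECMO or death on or before Day 60, documented in any study source (ordinal score, SAE form, follow-up after withdrawal), is an event even when Day 60 status is missing;
- only patients with no documented event and no Day 60 status are treated as missing;
- the number reclassified is reported by arm.

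Because results are already known, show this alongside both the complete-case analysis and the protocol's missing-as-event analysis. Keeping early events while leaving out event-free patients with incomplete follow-up slightly raises the observed proportions, which is a further reason to show all three. Also say which schedule governed in-hospital scoring after Day 14: 10.1, or the Schedule of Events and 9.2.4.

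The cost is derivation wording and a small table, using data that 8.3 and 11.1.3 already require. The sample size of 264 is unaffected. Asking at each contact about intubation since the last one would close the gap in a future study, but comes too late for this one.
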